### **Specific Aims**

**Aim 1:** Adapt a group-based prenatal intervention for pregnant Marshallese mothers (Kōmmour Prenatal) through culturally adapting an evidence-based prenatal intervention (Centering).

**Aim 2:** Conduct a feasibility/pilot test of Kōmmour Prenatal with up to 100 pregnant Marshallese women in Arkansas.

Aim 3: Compare the effectiveness on maternal and infant health outcomes between up to 100 pregnant Marshallese women provided Kōmmour Prenatal with the maternal and infant health outcomes of up to 100 pregnant Marshallese women who received individualized prenatal care. The provision of Kōmmour Prenatal is expected to demonstrate improved primary outcome of Gestational Weight Gain (GWG) and secondary outcomes of breastfeeding initiation; birthweight of infant, preeclampsia; primary cesarean birth; and GDM.

**Aim 4:** Explore the barriers and facilitators experienced by Clinical Staff and Marshallese Stakeholders who participate in the implementation of Kōmmour Prenatal with Marshallese women in Arkansas.

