### Data collection for Aim 3:

A systematic medical chart review will be used to document the primary outcome of GWG and secondary outcomes of: breastfeeding initiation; birthweight of infant, preeclampsia; primary cesarean birth; and GDM from women enrolled in Kōmmour Prenatal and those in individualized care. Medical chart review data for the up to 100 pregnant Marshallese women who received individualized prenatal care will be from participants in studies previously approved by the UAMS IRB where the participants agreed to their data being used in related studies. Birth record data and the linkage to ADH data will be used to assess maternal and infant health outcomes. It is necessary to use both medical birth record and de-identified data through ADH to receive disaggregated data to identify matching covariates for the analyses. These variables will include maternal age, parity, and sociodemographic variables. Propensity scores will be estimated using the variables available for both the Centering Pregnancy participants and the participants in [name] cohort study. Each Centering Pregnancy participant will be propensity score matched without replacement with a participant in

Version #:10 Page 10 Date: 20250403 IRB#261186

Maternal and Infant Health Outcomes of Marshallese in Arkansas

PI: [name]

Institution: University of Arkansas for Medical Sciences Northwest Campus

the cohort study using a nearest neighbor algorithm. Success of matching will be assessed by comparing covariate balance between groups using both standardized differences in covariate means and graphical displays of group differences. Logistic regression will be used to test for differences in the outcomes between the Centering Parenting and the comparison group. PASS 2020 was used for statistical power analyses. The primary analysis for Aim 3 will be a logistic regression with intervention status predicting a binary outcome.

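### The Aim 3 primary model names only intervention status, so imbalance that matching leaves in covariates that also predict the outcome passes into the primary estimate as written

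*Combined protocol and SAP*

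**What the plan says.** All of this is in the combined protocol and SAP, mainly under Data collection for Aim 3.

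- **Matching.** "Each Centering Pregnancy participant will be propensity score matched without replacement with a participant in" "the cohort study using a nearest neighbor algorithm". One comparison woman per intervention woman is implied. No caliper is stated. The scores are to use whichever variables both groups have.
- **Covariates.** Linkage to state birth records is needed to obtain "disaggregated data to identify matching covariates for the analyses". "These variables will include maternal age, parity, and sociodemographic variables".
- **Balance check.** "Success of matching will be assessed by comparing covariate balance between groups", by standardised differences and graphs. No threshold is given, and no step follows if balance is poor.
- **Primary model.** "The primary analysis for Aim 3 will be a logistic regression with intervention status predicting a binary outcome". The section's other mention of logistic regression also names no covariate, propensity score or pair term.
- **Comparison group.** Specific Aims refers to the "health outcomes of up to 100 pregnant Marshallese women who received individualized prenatal care". The Aim 3 section refers to "Medical chart review data for the up to 100 pregnant Marshallese women who received individualized prenatal care" and says these women come from previously approved studies. Neither place says whether this number is the pool before matching or the matched set.
- **General permission.** Study Design and Procedures says the state data will let demographic and socioeconomic covariates be used in analyses. It does not tie them to the Aim 3 primary model.

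**The concern.** This is the study's only between-group comparison, and the groups were formed differently. Intervention women are recruited into a group program, while comparison women were already enrolled in other studies. Matching is the only stated protection against confounding. Nearest-neighbour matching without replacement or caliper must find a partner for every intervention woman, however poor the match, so what it achieves depends on how many comparison women there are to choose from. A model with intervention status alone cannot correct what matching leaves behind. At stake is a first effectiveness estimate that partly reflects differences in age, parity or social circumstances, although those variables are already planned for collection.

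**Working it through.** The plan names its power software but gives no power, alpha, effect size or outcome rate, so there is no figure to reproduce.

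**Step 1: pool equal to the intervention group (no assumptions needed).** With 100 intervention women, a pool of 100, no replacement and no caliper, every comparison woman is used. A logistic regression on intervention status alone depends only on the 2×2 table of group by outcome. That table is the same before and after matching, so the estimate is the crude odds ratio.

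**Step 2: how large the bias could be (illustration).** Assumed, because the documents give none of these: no true effect, normal confounders shifted 0.25 or 0.50 SD between groups, slope 0.4 log-odds per SD, and a 50% outcome rate. To a first approximation the unadjusted odds ratio is exp(0.4 × sum of the signed residual imbalances in SD):

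- One confounder, nothing removed: exp(0.4 × 0.25) = 1.11; exp(0.4 × 0.50) = 1.22.
- Three acting the same way: exp(0.4 × 0.75) = 1.35; exp(0.4 × 1.50) = 1.82.
- Three with one reversed: the net shift equals that of one confounder, so again 1.11 and 1.22.

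The approximation runs slightly high because odds ratios shrink when covariates are omitted. Simulation of the planned algorithm (2,000 data sets per scenario, intervention-only model, robust standard errors) gave:

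| Intervention v pool | Confounders | Odds ratio at 0.25 / 0.50 SD | False positives |
|---|---|---|---|
| 100 v 100 | one | 1.10 / 1.21 | 6.6% / 12.0% |
| 100 v 100 | three, one reversed | 1.10 / 1.19 | 7.0% / 9.7% |
| 100 v 100 | three, same way | 1.31 / 1.73 | 16.4% / 51.3% |
| 80 v 100 | three, same way | 1.13 / 1.43 | 6.0% / 18.9% |
| 60 v 100 | three, same way | 1.05 / 1.25 | 4.9% / 9.7% |
| 100 v 200 | three, same way | 1.02 / 1.13 | 4.2% / 7.5% |
| 100 v 300 | three, same way | 1.00 / 1.06 | 4.1% / 4.9% |

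The mean imbalance left from 0.50 SD explains the pattern: 0.50 at 100 v 100, 0.32 at 80 v 100, 0.20 at 60 v 100, 0.13 at 100 v 200 and 0.06 at 100 v 300. For example, exp(0.4 × 3 × 0.13) = 1.17 against 1.13 simulated, and exp(0.4 × 3 × 0.06) = 1.07 against 1.06.

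**Step 3: a second set of assumptions.** With three covariates each shifted 0.30 SD and a combined outcome odds ratio of 1.5 or 2.0 per SD (600 data sets each), a pool of 100 left the 0.30 SD unchanged and gave 1.23 (12.2% false positives) and 1.39 (19.2%). A pool of 200 left about 0.035 SD (odds ratios 1.02 to 1.03), and a pool of 300 about 0.012 SD (1.00 to 1.03).

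**Step 4: adding the covariates.** With every propensity covariate in the outcome model, odds ratios were 0.98 to 1.02 and false positives 4.0% to 6.2% over the 48 scenarios of Step 2's design. The adjusted model there has the form that generated the data, so this is the favourable case.

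**Step 5: leaving one out.** With four equally strong confounders and one omitted from the adjusted model, 100 v 100 gave 1.11 / 1.22. A partial covariate list is therefore not enough when matching removes nothing.

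**The case against.** The strongest reply has four parts.

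- *The sentence is not a full model statement.* It follows directly on the mention of power software and may only name the model that was powered, and covariates are permitted elsewhere. This stands in part. A reader might infer that the plan rules out adjustment, but the documents do not support that. They leave the covariates unassigned, so the primary estimate could be produced either way.
- *The comparison group is probably drawn from a larger source.* The text speaks of matching to a participant in a cohort study and of previous studies in the plural, and the figure of up to 100 mirrors the intervention group. That is a fair reading, and under it the bias is small. A reader might infer that the matching is bound to be empty; the documents do not support that either. They do not establish that the pool is large.
- *The sizes are invented.* They are assumptions. The 1.73 and 51.3% need three confounders at 0.50 SD, all biasing the same way, with no spare comparison women. It is also tempting to say that any measured imbalance biases the estimate. Only imbalance in covariates that also predict the outcome does so, and the documents give no such associations.
- *A balance check is planned, and a caliper or re-matching would be other remedies.* True, but none is written down, and a check with no consequence leaves the estimate as it is.

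**Conclusion.** The point holds and should be fixed before analysis. As written, the primary Aim 3 estimate carries whatever imbalance matching leaves in outcome-predicting covariates, and nothing in the plan responds to it. If the pool is about 100 and about 100 intervention women enrol, matching removes nothing. If the pool is 2 to 3 times larger, little remains. The first statement follows from the algorithm; every odds ratio and error rate above rests on assumed imbalances, slopes and outcome rates. Study Design and Procedures describes the goal as preliminary effectiveness, so the gain is a more trustworthy first estimate rather than a corrected confirmatory test. A reader should not conclude that adjustment makes the comparison unconfounded: unmeasured self-selection into group care remains under either model.

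**What to change.** State that the primary Aim 3 logistic regression, fitted on the matched sample, includes intervention status and the same covariates used in the propensity model: maternal age, parity and the prespecified, named sociodemographic variables. If outcomes are too rare for that many terms, include the key covariates plus the logit of the estimated propensity score (this fallback was not simulated). Report the number of comparison women available for matching and the post-match standardised differences.

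The cost is a sentence or two of plan text and a changed model statement, using data already planned for collection. The downsides are:

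- **Precision.** At 100 v 100 with three covariates, the standard error of the log odds ratio rose from about 0.29 to 0.31–0.33. Power did not fall in the illustration: for a true odds ratio of 0.45 with no imbalance, it was 70.0% without and 73.2% with covariates.
- **Interpretation.** The odds ratio becomes conditional on the covariates, and the report should say so.
- **Rare outcomes.** At a 5% comparison-group rate, 7 of 1,000 fits failed with 6 covariates and 10 of 1,000 with 10. The mean standard error was about 11% too small (0.726 against an empirical 0.819, and 0.757 against 0.855). This is the reason for the fallback.
- **Timing.** Study Timeline puts enrolment in months 4–16 from January 2021, so to about April 2022, and this version is dated April 2025. Whether outcomes have been examined is not stated. Report the date on which the covariate list was fixed.

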### **Background and Rationale**

Pacific Islanders residing in the United States (US) have disproportionally higher rates of preterm birth (<37 completed weeks) and low birthweight infants (<2,500 grams). They are also more likely to experience preeclampsia, primary cesarean birth, excessive gestational weight gain, gestational diabetes mellitus (GDM) and low exclusive breastfeeding initiation and duration at six months compared to other racial/ethnic minorities and the US population in general.  Preterm birth is a pressing challenge to maternal, infant, and child health in the US because preterm infants can face lifelong disabilities and are at higher risk of death during their first few days of life.  Early and consistent prenatal care is strongly associated with positive birth outcomes and is a global health priority.  However, Pacific Islanders, are less likely to receive early and consistent prenatal care compared to other racial/ethnic groups and are thus at a higher risk for maternal and infant health disparities. 

Pilot analysis of Arkansas birth records (n=2,488) has shown that Marshallese in Arkansas experience a high rate of adverse perinatal outcomes: 15% of Marshallese women received no prenatal care (compared to 1.6% women nationally); More than 50% do not attend the recommended number of prenatal care visits; 19% of Marshallese infants were born preterm (compared to 9.6% nationally), and 15% of Marshallese infants were low birthweight (compared to 8.3% nationally). Additionally, qualitative data, demonstrate that Marshallese women experience numerous structural barriers that constrain prenatal care such as negotiating health insurance, transportation, and language barriers. Social-cultural barriers include a lack of understanding of the importance of seeking early and consistent prenatal care, feelings of shame and embarrassment, perceived discrimination from prenatal care providers, and an overall fear of the process.

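### Gestational weight gain and birthweight are measured quantities, but the plan analyses them only by logistic regression, with the primary analysis on a binary outcome it never names

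*Combined protocol and SAP*

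**What the plan says.** Specific Aims, Aim 3, expects the programme to show "improved primary outcome of Gestational Weight Gain (GWG) and secondary outcomes of breastfeeding initiation; birthweight of infant, preeclampsia; primary cesarean birth; and GDM". GWG and birthweight are measured quantities; the other four outcomes are yes/no events.

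The section Data collection for Aim 3 gives one model for all of them: "Logistic regression will be used to test for differences in the outcomes between the Centering Parenting and the comparison group". It closes with: "The primary analysis for Aim 3 will be a logistic regression with intervention status predicting a binary outcome". It does not say which outcome this is or what counts as an event, and it describes no model for a continuous outcome.

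The nearest text is in Background and Rationale. It lists "excessive gestational weight gain" among the problems seen in Pacific Islanders, without a threshold and without a link to the endpoint. For birthweight it does supply a cut, "low birthweight infants (<2,500 grams", but the Aim 3 section does not adopt it.

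The chart-abstraction list under Study Design and Procedures includes maternal weight and height with no time point. Appendix 1 lists weight at delivery and an item verifying pre-pregnancy weight. Neither is named as the start or end of GWG. Comparison women come from "participants in studies previously approved by the UAMS IRB where the participants agreed to their data being used in related studies".

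**The concern.** A primary analysis should follow from its primary outcome without a further decision. Here three decisions remain: the weight from which gain is counted, the cut that turns gain into an event, and which side of the cut is the good one. Improvement could mean less gain, less gain above a limit, or more women within a range, and these can give different answers from the same data. Unless the choice is fixed and dated, a reader of the results cannot tell whether the reported primary result is the planned one.

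There is also a cost in efficiency. With at most 100 women per group, reducing a measured outcome to two categories gives up precision that the study can hardly spare.

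**Working it through.** **Nothing to reproduce.** The plan names the power software but gives no alpha, power, event rate, SD or effect size. All figures below are illustrations.

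**Inputs from the protocol.** Up to 100 women per group (Aim 3); 15% low birthweight among Marshallese infants and the 2,500 g definition (Background and Rationale).

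**Assumptions.** Two-sided 5% test, normal outcome, intervention effect a pure shift of 0.40 SD, pairing ignored, and a two-proportion test standing in for unadjusted logistic regression.

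**1. Measured scale.** Power = Φ(d√(n/2) − 1.96) = Φ(0.40 × √50 − 1.96) = Φ(2.83 − 1.96) = Φ(0.87) ≈ 81%.

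**2. Same shift after a cut.** If a share p₁ of controls exceeds the cut c = Φ⁻¹(1 − p₁), the intervention share is p₂ = 1 − Φ(c + 0.40). With p̄ the mean of the two, power = Φ{[|p₁ − p₂| − 1.96√(2p̄(1 − p̄)/n)] / √[(p₁(1 − p₁) + p₂(1 − p₂))/n]}.

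| Controls above cut | Intervention above cut | Power |
|---|---|---|
| 20% | 10.7% | 44% |
| 30% | 17.8% | 53% |
| 40% | 25.7% | 58% |
| 50% | 34.5% | 61% |

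**3. Birthweight at 2,500 g.** The efficiency of a cut relative to the measured scale is φ(z)²/[p(1 − p)] for a small shift. At p = 0.15, z = −1.036 and φ(z) = 0.2332, so the efficiency is 0.0544/0.1275 = 0.426, a loss of about 57%.

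**4. Does the choice of event matter?** Suppose controls are 25% below, 25% within and 50% above some range (assumed). The same 0.40 SD downward shift then gives:

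- above range: 50% to 34.5%, power about 61%, read as benefit;
- below range: 25% to 39.2%, power about 58%, read as harm;
- within range: 25% to 26.4%, power about 6% counting both tails, read as nothing.

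**5. Where the measured scale does worse.** Suppose the means are equal, the SD is 30% smaller under the intervention, and the target range is ±1 control SD. The share in range is 2Φ(1) − 1 = 68.3% against 2Φ(1/0.7) − 1 = 84.7%. The binary test has about 79% power at 100 per group; the comparison of means has about 5%.

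**6. Hypothetical only: several codings tried and the best reported.** In null simulations at 100 per group over a set of assumed category splits, the two-sided false-positive rate was about 9% for two codings (above range, within range) and 12% to 13% for three (adding below range).

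**The case against.** **The study is a pilot.** Study Design and Procedures speaks of preliminary effectiveness, the comparison is non-randomised, and no alpha or decision threshold is given. This stands as far as confirmatory error claims go. It does not remove the need for a definition: Aim 3 sets out to "Compare the effectiveness on maternal and infant health outcomes", names a primary outcome and declares a primary analysis.

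**Logistic regression on categorised GWG is ordinary practice, and the Background hints at excess gain.** The first part is correct. The fault is that the event is unstated, and that no analysis on the measured scale is offered for a measured outcome. The hint carries no threshold and does not mention the endpoint.

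**Naming the formula and one binary event would be enough.** That would make the analysis runnable. It would leave the loss of information in place, and moving to the measured scale costs almost nothing.

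**Stronger readings a reader might infer, which the documents do not support:**

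- *The false-positive rate is 9% to 13%.* These rates require several codings to be tried and the best reported. Nothing in the documents shows that this was done or is planned, and the category splits are assumed.
- *GWG cannot be computed, because women may enrol in any trimester or because Appendix 1 lacks a pre-pregnancy weight value.* GWG is to come from chart review, and a chart read after birth can still hold an early weight. Late enrolment does not remove it. What is missing is the rule for choosing one weight. Appendix 1 is only a reason to check.
- *The event was, or will be, chosen after the data were seen.* The version is marked "Date: 20250403", which is month 52 counting January 2021 as month 1, and enrolment was planned for months 4 to 16. Those are planned dates. Actual enrolment dates are not given, and a version date does not show when this text was written or what had been examined.

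**Conclusion.** The point holds as a mismatch between outcome and analysis, and should be corrected before Aim 3 is analysed. The primary outcome is measured, the only model is logistic, and the event, starting weight and direction are absent. This follows from the text and rests on no assumed figure.

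The size of the loss does rest on assumptions. Under normality and a pure shift, with pairing ignored and the full 100 per group, power for 0.40 SD falls from about 81% to between 44% and 61%; for birthweight about 57% of the information is lost at the 15% rate. The actual loss for GWG cannot be computed, because the protocol gives no GWG category rate. If the effect were on spread rather than mean, the comparison would reverse.

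**What to change.** In Data collection for Aim 3:

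1. Define GWG as the last weight before delivery minus one named starting weight, with the same rule in both groups, and state what improvement means.
2. Make the primary analysis a linear regression of GWG on the measured scale in the matched sample, adjusted for the matching covariates and for starting weight or BMI where both groups have it.
3. Report one fixed, stated binary GWG definition by logistic regression as supportive.
4. Analyse birthweight in grams by linear regression, with below 2,500 g as supportive.
5. Keep logistic regression for preeclampsia, primary cesarean birth, GDM and breastfeeding initiation.
6. Date the change and state which outcome data, in either group, had already been seen. If GWG has been examined, say so and label the analysis accordingly.

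The cost is protocol wording, the dated statement, and a check that a usable starting weight exists in both groups. The drawback is that a mean difference is less tied to a clinical category and can miss a change in spread, which is why the fixed binary analysis is kept.

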Current health care interventions are not culturally relevant or focus primarily on individual-level motivations that are not effective within highly collectivistic Pacific Islander cultures.  Pacific Islander communities' concepts of health and wellbeing are largely shaped by collectivistic cultural values and practices, suggesting the need for culturally adapted group-based interventions.  Recent data with other cultural groups report that pregnant women who received a group-based prenatal intervention (Centering Pregnancy) had a significantly lower risk of having a preterm birth, low birth weight infants, and improved outcomes with GDM compared to women receiving individualized care.  However, group prenatal care has not been culturally adapted and tested with the Marshallese or other Pacific Islanders in the mainland US.

From 2000 to 2010, the Pacific Islander population in the US increased by 40%, growing three times faster than the total US population and making it the second-

 Version #:10
 Page 3

 Date: 20250403
 IRB#261186

Maternal and Infant Health Outcomes of Marshallese in Arkansas

PI: [name]

Institution: University of Arkansas for Medical Sciences Northwest Campus

fastest-growing population in the US. The fastest growth occurred in the South (66%), especially in Arkansas (252%), where the majority of Pacific Islanders are Marshallese. Arkansas has the largest population of Marshallese living in the continental US (~14,000 people). Since the Pacific Islander population is small, some argue that the Pacific Islander population should be given less consideration for funding than other racial and ethnic groups; this faulty logic has directly contributed to the stark health disparities experienced by this population. Pacific Islanders are underrepresented in research and receive far less investment than other disparate populations (both in total and in proportion to their population numbers). Overall, limited scientific knowledge, masked health disparities due to data aggregation of Pacific Islanders with other Asian groups, and a lack of resource allocation for research and programs are critical barriers to progress in addressing Pacific Islanders' health disparities.

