### **Study Design and Procedures**

A mixed methods design will be utilized to explore the feasibility and preliminary effectiveness of Kōmmour Prenatal among pregnant Marshallese women. Potential participants may be recruited from UAMS centering programs, including mobile centering, across the state.

Participants will be invited to take part in a focus group and survey prior to attending up to 10 group prenatal sessions (Kōmmour Prenatal). Participants will also be invited to take part in both the survey and qualitative focus groups at the end of the intervention. The surveys will capture demographics, health behavior and health belief information. The focus groups will focus on beliefs and experiences of individualized and group prenatal care, prenatal care satisfaction, and health behaviors. Study procedures (e.g., consent process, focus groups, surveys, data collection, administering compensation) will be conducted in person or remotely. In either case, tools such as phone, video, email, text, and online data collection tools (e.g., REDCap) may be used.

Due to difficulty with in-person data collection, remote date collection via Zoom will be utilized to collect focus groups and surveys when in-person data collection is not feasible for the participant.

 Version #:10
 Page 5

 Date: 20250403
 IRB#261186

Maternal and Infant Health Outcomes of Marshallese in Arkansas

PI: [name]

Institution: University of Arkansas for Medical Sciences Northwest Campus

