## Study Schedule for women in Kommour Prenatal

For pregnant women enrolled in Kōmmour Prenatal, the first survey and focus group will take place at enrollment. Participants will attend up to 10 group prenatal sessions. Another survey and focus group will take place in the third trimester (6-9 months of pregnancy). Data abstraction from birth and medical records will take place after the birth for information of both the postpartum participant and her infant.

Data Collection-Pregnant Women in Kommour Prenatal

 Version #:10
 Page 7

 Date: 20250403
 IRB#261186

Maternal and Infant Health Outcomes of Marshallese in Arkansas

PI: [name]

Institution: University of Arkansas for Medical Sciences Northwest Campus

Enroll	First trimester	Second Trimester	Third trimester	Six Weeks Postpartum
Enrolled in study	X	Х	Х	
10 Group-Prenatal Intervention	Х	Х	Х	
Medical record abstraction	Х			Х
Birth record abstraction				Х
Focus group	Х	Х	Х	
Survey questionnaire	Х	Х	Х	

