### **Data Analysis**

### Data collection and analysis for Aim 2:

A mixed-methods design will be used to determine the feasibility of Kōmmour Prenatal to improve adherence to recommended prenatal care visits and prenatal care satisfaction. After consent, and prior to the first focus group, participants will be asked to complete a survey. The survey may be completed in person or electronically via a link to REDCap. After participants have completed the survey, we will begin the focus group. Within the focus group, participants will be reminded to not disclose the identity of others who are participating or any information discussed. Focus groups will take place in a private room of a community-based organization- e.g. Jones center, hospital, UAMS-NW, local community church, or remotely using phone or a secure technology such as Zoom or Skype.

After the participants have provided consent and completed their first survey and focus group, participants will begin a series of up to 10 group prenatal sessions (Kōmmour Prenatal).

At third trimester participants will be asked to participate in an additional survey and focus group focused on their experiences in this intervention. Consistent with the first focus group, participants will be reminded to not disclose the identity of others who are participating or any information discussed. Focus groups will take place in a private room of a community-based organization- e.g. Jones center, hospital, UAMS-NW, local community church, or remotely using phone or a secure technology such as Zoom or Skype.

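### The primary Aim 3 logistic regression states no variance allowance for women who share prenatal groups, so positive within-group correlation would make its standard error understate the intervention-arm variance

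*Combined protocol and SAP*

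**What the plan says.** Under Data collection for Aim 3, the test between arms is described twice: "Logistic regression will be used to test for differences in the outcomes between the Centering Parenting and the comparison group", and then "The primary analysis for Aim 3 will be a logistic regression with intervention status predicting a binary outcome". Neither sentence names a variance method. The same section sets up the comparison by matching: "Each Centering Pregnancy participant will be propensity score matched without replacement with a participant in" the cohort study, with a nearest-neighbour algorithm. I read this as one comparison woman per intervention woman.

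The two arms receive care in different forms. Under the Aim 2 analysis, after consent and the first survey and focus group, "participants will begin a series of up to 10 group prenatal sessions"; the Study Schedule agrees ("Participants will attend up to 10 group prenatal sessions"). Aim 3 under Specific Aims sets these women against "up to 100 pregnant Marshallese women who received individualized prenatal care". Study Design and Procedures adds a possible further level: "Potential participants may be recruited from UAMS centering programs, including mobile centering, across the state".

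The document does not mention clustering, ICC, random effects, generalized estimating equations, robust variance or a design effect. It names the software used for power but gives no inputs or result. It does not give the number or size of prenatal groups, or say whether membership is closed or rolling.

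**The concern.** A plain logistic regression treats every woman as an independent observation. Women in one prenatal group share sessions, facilitators and peers, and perhaps a site. If that makes their outcomes more alike, 100 women in groups carry less information than 100 independent women, and the model-based standard error does not show it. The interval would then be too narrow and the test would reject too often under the null, unless something offsets it.

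The Background argues for group delivery from the community's collectivistic values, "suggesting the need for culturally adapted group-based interventions". That fits with group members influencing one another, but the firmer basis for suspecting correlation is simply that the women share sessions.

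Aim 3 has a named primary outcome and a formal test between arms, so the validity of the standard error matters even in a study that is otherwise about feasibility.

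**Working it through.** **Inputs from the protocol:** up to 100 women per arm (Aim 3); group sessions in one arm and individualized care in the other; matching without replacement; logistic regression on arm. There is no stated power, alpha or sample-size calculation to reproduce.

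**Inputs assumed, none of them in the documents:** two-sided 5%; exactly 100 v 100; closed, equal groups with m study women each; a given ICC; independent comparison women; correlation r between the outcomes of the two women in a matched pair.

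**Formulas.** The intervention-arm design effect is DE = 1 + (m − 1) × ICC. With equal arms and equal event rates under the null, the true variance of the contrast relative to the model-based variance is V = (DE + 1)/2 − r. The true standard error is √V times the model-based one, and the actual type I error is 2[1 − Φ(1.96/√V)].

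**Example, m = 10, r = 0.**
- ICC 0.02: DE = 1 + 9 × 0.02 = 1.18; V = 2.18/2 = 1.09; √V = 1.044; type I error 6.05%. Effective intervention n = 100/1.18 = 85.
- ICC 0.05: DE = 1 + 9 × 0.05 = 1.45; V = 2.45/2 = 1.225; √V = 1.107; type I error 7.66%. Effective n = 100/1.45 = 69.

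**Range, r = 0 (type I error, %):**

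| m | ICC 0.01 | 0.02 | 0.05 | 0.10 |
|---|---|---|---|---|
| 3 | 5.11 | 5.23 | 5.58 | 6.17 |
| 5 | 5.23 | 5.46 | 6.17 | 7.36 |
| 10 | 5.52 | 6.05 | 7.66 | 10.36 |
| 12 | 5.64 | 6.28 | 8.26 | 11.54 |

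The row m = 3 stands for groups that consist mostly of women outside the study. At ICC 0 every entry is 5.0%. Rolling membership would also lower the figures.

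**Offset from matching, m = 10.**
- ICC 0.05: r = 0.10 gives V = 1.225 − 0.10 = 1.125 and 6.5%; r = 0.20 gives V = 1.025 and 5.3%.
- ICC 0.02: r = 0.10 gives V = 0.99 and 4.9%; r = 0.20 gives V = 0.89 and 3.8%.

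**Check by simulation** (beta-binomial groups, 10 groups of 10 v 100, assumed 30% event rate, no pair correlation, 40,000 runs per setting), rejection rate in %:

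| ICC | 0 | 0.02 | 0.05 | 0.10 |
|---|---|---|---|---|
| Plain Wald test | 4.9 | 6.0 | 7.6 | 10.5 |
| Cluster-robust CR2 with Satterthwaite t | 4.7 | 4.8 | 4.8 | 5.2 |

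The plain test agrees with the formula and the corrected test holds its level. At a 50% event rate the plain test gives 5.6% even at ICC 0, which is discreteness of the test and not clustering. With 5 groups of 10 v 50, the same corrected standard error rejects 6.0% to 7.1% against a normal reference and 3.9% to 4.8% against the t, so the t reference is needed.

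**Both dependences together** (10 groups of 10, ICC 0 to 0.10, r 0 to 0.20): clustering on group alone rejects 2.7% to 5.2%; two-way clustering on group and pair rejects 4.7% to 5.8%.

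**The case against.** The strongest reply is that the net error could be nil or in the safe direction. Matching is the one dependence that the Aim 3 section itself creates, and positive correlation within pairs makes the plain test conservative. At ICC 0.02 and m = 10, r = 0.10 is enough to bring the test just under 5%. The largest figure in the table needs groups of 12, an ICC of 0.10, closed membership and no pair correlation all at once. This stands. It rules out a claim about the net direction, but two unaddressed dependences cannot be relied on to cancel.

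A reader might infer three stronger things that the documents do not support:
- That the planned test is anti-conservative. Group size, number of groups, stability of membership, ICC and pair correlation are all absent, so this cannot be shown.
- That the collectivism argument establishes within-group correlation. It describes the Marshallese community as a whole, so it applies to comparison women too, and it says nothing about likeness within a particular group.
- That comparison women are certainly independent. They come from earlier studies and may share clinics or providers. What the documents do support is that they did not share this programme's prenatal groups.

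It can also be said that this is a feasibility study, and that the text is silent on robust variance and does not exclude it. Both are true and limit the weight of the point. But Aim 3 still plans a formal comparison, and a logistic regression run as written would use the model-based standard error.

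**Conclusion.** The point holds in conditional form. The plan states no variance allowance for shared prenatal groups, and if within-group correlation is positive, the model-based standard error understates the intervention-arm variance. Under the assumptions of 100 v 100, closed groups of 10, ICC 0.02 to 0.05 and no pair correlation, type I error is about 6% to 7.7%. It is close to 5% with few study women per group or a low ICC. Positive pair correlation could cancel or reverse the effect, so the net direction is open. The omission is certain and its size is not, so this is a change the sponsor should make and not a flaw that invalidates the comparison.

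**What to change.** - **Record the group.** Hold a coded prenatal-group identifier for each intervention woman. It is not among the items listed for medical record abstraction in Study Design and Procedures. Enrolment was planned for months 4 to 16 from January 2021, and this version is dated April 2025, so the code may have to be recovered from programme attendance records. This must be done before the permanent de-identification described under Data Handling and Recordkeeping. State in advance how a woman who changed groups is assigned.
- **State the variance.** Keep the same odds ratio. Report it with a cluster-robust standard error with the CR2 correction and a Satterthwaite t reference, taking prenatal group as the cluster in the intervention arm and each comparison woman as her own cluster.
- **Address the matching.** Also report a variance that accounts for both group and matched pair, and say in advance which of the two is primary. In the simulations the two-way version was closer to 5% when pairs were correlated.
- **Describe the groups.** Report their number and size and the estimated ICC.
- **Site.** Collect a site code only if site enters the variance or a stated sensitivity analysis.

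**Cost.** No extra participants or visits, but some work to recover group membership. Intervals widen. At m = 10 the t reference has about 33 degrees of freedom, with a 97.5% point of about 2.03, so the interval is about 2.03/1.96 = 1.04 times as wide even at ICC 0. With the larger standard error, the simulated widening is about 8% at ICC 0.02 and 15% at ICC 0.05. It is 3% to 4% with three study women per group at the same ICCs, and up to about 31% with 8 groups of 12 to 13 at ICC 0.10. If pairs are positively correlated and only group is used, the test is conservative (down to 2.7% in the settings simulated).
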